### **Statistical Methods**

STEP 1 and 2:

Sleep variables from questionnaires (subjective) and actigraphy/WatchPAT (objective) including sleep duration, sleep quality and sleep apnea will be analyzed to explore their relationship with HbA1c, and when available, fasting glucose and insulin levels. Bivariate analysis will be used. To identify the independent sleep predictor of glucose tolerance status, multivariate regression analysis will be employed.

STEP 3:

Area under the curve of GLP-1 and its peak response will be compared between short and normal sleepers.

Power/Sample Size:

STEP 1: The sample size of 600 was selected to follow a rule of 10 participants for each variable in the multivariate regression analysis. Predictors of HbA1c include age, sex and BMI. Sleep predictors will include sleep duration, quality and sleep apnea risk. In addition, the sample size was chosen to ensure adequate recruitment of short sleepers (based on prevalence of 20-25%) into STEP 2 and 3.

STEP 2: The sample size of 80 in step 2 was chosen to ensure adequate recruitment for STEP 3 which requires 62 participants, with a 75% concordance rate of self-reported and objectively measured sleep duration

STEP 3: Based upon a sample size of n=31 patients per group, this study has 80% power to detect a 35% difference in the peak time of GLP-1 between groups GLP-1 level with a 10% drop out rate. This calculation is based on data of a previous study of acute sleep deprivation and GLP-1 response (11).

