Insufficient sleep has been linked to reduced insulin sensitivity and increased risk of type 2 diabetes, both in laboratory studies in healthy humans and in epidemiologic studies. A causative role of partial sleep restriction in promoting alterations in glucose metabolism was first established in 1999(1). Intravenous glucose tolerance testing (IVGTT) following sleep restriction to 4 hours per night(h/night) for 5 nights resulted in a 24% decrease in insulin sensitivity as well as a 30% decrease in the acute insulin response to intravenous glucose(1,2). Multiple cross sectional epidemiologic studies have indicated that short sleep duration (usually < 6 h/night) is associated with increased impaired glucose tolerance and diabetes risk(3). A recent meta-analysis including 7 of these 10 studies (total 107,756 participants concluded that short sleep ( $\square$  5-6 h/night) predicts the development of type 2 diabetes with a pooled relative risk (RR) of 1.28(4). There are only a few studies examining the impact of insufficient sleep on glycemic control in patients with established type 2 diabetes. A questionnaire survey study of 161 African Americans with type 2 diabetes found that 3 hours of perceived sleep debt per day (i.e. a self-report of insufficient sleep duration) predicted a HbA1c level of 1.1% above the median(5). The magnitude of this difference is comparable to the effect size of several FDA-approved diabetes medications. Recently, a large cross sectional study of 4,870 Japanese participants revealed a U-shaped relationship between sleep duration and glycemic control, with higher HbA1c levels in patients with self-reported sleep duration <5.5 h/night and  $\square$  8.5 h/night compared to those with 6.5-7.4 h/night (6). These data support a role of sleep duration on glycemic control in patients with type 2 diabetes. However, the assessments of sleep duration in these studies were done subjectively i.e. by questionnaires. The only study which assessed the relationship between glycemic control (HbA1c) utilizing objective sleep measurement by actigraphy revealed that only sleep fragmentation, but not sleep duration, was associated with higher HbA1c level (7).

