In addition, other aspects of sleep disturbances have also been shown to affect glucose control in patients with type 2 diabetes, including poor sleep quality(8) and the severity of untreated OSA (9). Therefore, the independent role of sleep duration and glycemic control requires further investigation. Whether the relationship extends to those with prediabetes is unknown. We hypothesized that prediabetes patients with short sleep duration, as measured objectively, will have worse glucose tolerance than those with normal sleep duration.

GLP-1 is an important incretin hormone which plays a role in regulating postprandial glucose excursion and appetite regulation. The role of sleep in GLP-1 regulation was explored in a few experimental studies in healthy human. Sleep restriction to 4 hours per night in healthy participants resulted in lower GLP-1 levels in the afternoon in women (10). In addition, total sleep deprivation in healthy participants resulted in a delayed GLP-1 response to breakfast (11). Sitagliptin treatment for 12 months in patients with type 2 diabetes resulted in 0.6% decrease in HbA1c as well as improved sleep quality as assessed by questionnaire (12). The role of GLP-1 response in patients with prediabetes who are short sleepers has not been explored. We hypothesize that those with chronic short sleep will have a lower or delayed GLP-1 response to meal compare to those with normal sleep duration. If this is proven, GLP-1 therapy may especially be effective in improving glycemic control in patients with abnormal sleep. Since the current proposed study is exploratory in nature by means of association, future interventional trial will be needed to show the causal relationship between GLP-1 and sleep.

Therefore, the aims of the current study are to explore the relationship of sleep duration and glucose tolerance in patients with prediabetes, as well as the effects of chronic short sleep duration on GLP-1 response to meals in these patients

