**Hypothesis**

1. Prediabetes patients who have insufficient sleep will have worse glucose tolerance than those with normal sleep duration.
2. Prediabetes patients with short sleep will have a delayed or reduced GLP-1 response to a standardized meal

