**Study Design/Population/Method**

The study has three components;

Step 1: Questionnaire study of 600 patients with prediabetes. The questionnaires will capture subjective sleep measurements and eating habits.

Step 2: Participants ages 40-65 reporting short sleep duration ( $\leq 6$  h/night) and normal sleep duration (7-8 h/night) will undergo objective sleep measurements including sleep duration, sleep quality and obstructive sleep apnea. This step will serve as a screening for step 3 (expected N= 80).

Step 3: Study to compare GLP-1 response to standard mixed meal test in patients with chronic short sleep and those with normal sleep duration. (n= 31 in each group).

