## Study Procedures/Study Flowchart

### STEP 1

After informed consents are obtained, the participants will be interviewed regarding their medical history and sleep schedules on weekdays and weekends, as well as other aspects of sleep, mood and dietary habits. Standardized questionnaires will be utilized, including Morningness-Eveningness questionnaire (13) Pittsburg Sleep Quality Index to assess sleep quality (14), Berlin Questionnaire to assess risk of sleep apnea(15), depressive symptoms (CES-D)(16), Epworth Sleepiness Scale to assess daytime sleepiness (17), and review of dietary intake in the past 24 hours (24 hour food recall).

Medical records will be reviewed to collect data regarding medication use.

Weight, height, hip and waist circumference as well as neck circumference will be measured.

Blood sample will be obtained for hemoglobin A1c levels within 6 months of an interview if not done in the prior 6 months. Additionally, blood sample will be saved for possible further genetic and metabolic analyses.

### STEP 2

Those between ages 40-65 years who reported short sleep (≤6h/day) and normal sleep (7-8 h/day) will undergo objective sleep measurements as follow. Expected participants = 80

Participants will wear Actiwatch (Respironics, USA) at home for 1 week. Actiwatch is a small, watch-like device which can measure sleep timing and quality, daytime activities as well as light exposure.

Participants will wear the device on their non-dominant wrist and instructed not to wear clothes which sleeves may cover the watch. The device is water resistant.

During this week, the participants will keep a record of their sleep schedules and dietary intake.

On the last morning of actiwatch wearing, participants will collect overnight urine for urine melatonin measurements. They will fast after midnight and return to the hospital to have blood sample taken for fasting glucose and insulin, as well as return the actiwatch device.

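### The hypothesis concerns objectively measured sleep, but the 600-patient regression can use only self-report, and the Step 2 self-report/actigraphy pairs are not used to link the two analyses

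*Combined protocol and SAP*

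**What the plan says.** - Background and Rationale states: "We hypothesized that prediabetes patients with short sleep duration, as measured objectively, will have worse glucose tolerance than those with normal sleep duration". It also criticises earlier work in type 2 diabetes: "However, the assessments of sleep duration in these studies were done subjectively i.e. by questionnaires".
- The Hypothesis section repeats the first hypothesis without a measurement method: "Prediabetes patients who have insufficient sleep will have worse glucose tolerance than those with normal sleep duration". Objective 1 names none either.
- For Step 1 (600 patients), Study Design/Population/Method says: "The questionnaires will capture subjective sleep measurements and eating habits".
- Objective measurement comes only in Step 2 (expected N = 80): "Participants will wear Actiwatch (Respironics, USA) at home for 1 week". The Step 2 population is aged 40-65, takes no diabetes medication, and reports either short sleep or 7-8 h.
- Statistical Methods, Steps 1 and 2, says: "Sleep variables from questionnaires (subjective) and actigraphy/WatchPAT (objective) including sleep duration, sleep quality and sleep apnea will be analyzed". The outcomes are HbA1c and, where available, fasting glucose and insulin; the methods are bivariate analysis and multivariable regression. It names no primary exposure or sample and no calibration or measurement-error analysis.
- Under Power/Sample Size, the 600 is justified by the multivariable regression, with age, sex, BMI, sleep duration, sleep quality and apnea risk as predictors. Step 2 is sized to feed Step 3, "with a 75% concordance rate of self-reported and objectively measured sleep duration".

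**The concern.** The regression that the 600 is sized for uses the kind of sleep measurement that the rationale faults in earlier studies. The actigraphy analysis matches the rationale but rests on about 80 people. The two may disagree, and the plan gives no way to reconcile them.

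At stake is the interpretation of Step 1. If self-report is an imperfect stand-in for objective duration, a small or null Step 1 coefficient could be reported as no independent role of sleep duration when exposure error is part of the reason. The Step 2 participants have both measures and are drawn from Step 1, so they form an internal validation sample that the plan leaves unused for this purpose.

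**Working it through.** **1. What the 75% is used for.** It appears only in the sizing of Step 2. Expected yield is 80 × 0.75 = 60, against 62 required. Strict inflation gives 62/0.75 = 82.7, so 83; the looser 62 × 1.25 = 77.5, so 78. The stated 80 is thus a rounded recruitment figure. Nothing in the text makes 75% an error rate for the 600, and concordance is not defined.

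**2. Attenuation if the 75% were an agreement rate.** For a two-group contrast with non-differential error and no covariates, with actigraphy as reference:
- 75% of each report group confirmed, all others truly in the opposite group: 0.75 + 0.75 − 1 = 0.50.
- All others at 6-7 h with half the effect: (0.75 + 0.25 × 0.5) − (0.25 × 0.5) = 0.75.
- 75% read as sensitivity and specificity, at the plan's 20-25% prevalence of short sleep. At 20%: PPV = 0.15/(0.15 + 0.20) = 0.429, NPV = 0.60/(0.60 + 0.05) = 0.923, factor 0.35. At 25%: PPV = 0.50, NPV = 0.90, factor 0.40.

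The illustrative range is therefore about 0.35 to 0.75.

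**3. Direction.** With one exposure and classical error the slope shrinks: a true 0.10 becomes 0.05 at reliability 0.5. But sleep quality and apnea risk are also questionnaire-based in Step 1. With two standardised covariates, the observed slopes are (Σ_X + Σ_error)⁻¹ Σ_X β. Assume true slopes of 0.10 (sleep) and 0.30 (apnea) and correlation 0.5, so Σ_X β = (0.25, 0.35).
- Sleep reliability 0.75, apnea reliability 0.5: (2 × 0.25 − 0.5 × 0.35)/(1.333 × 2 − 0.25) = 0.325/2.417 = 0.134, away from zero.
- Sleep reliability 0.5, apnea measured without error: (0.25 − 0.5 × 0.35)/(2 − 0.25) = 0.075/1.75 = 0.043, towards zero.

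**4. What the Step 2 pairs could add.** Assumed, not from the documents: 135 short and 255 normal reporters, 40 + 40 of them with actigraphy, true difference 0.30 SD, outcome SD 1, no covariates. The standard errors below ignore uncertainty in the factor itself.

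| | Others in opposite group | Others midway |
|---|---|---|
| Uncorrected Step 1 estimate | 0.30 × 0.50 = 0.15 | 0.30 × 0.75 = 0.225 |
| SE, uncorrected | √(1/135 + 1/255) = 0.106 | about the same |
| SE, actigraphy only | √(2/40) = 0.224 | √(2/30) = 0.258 |
| SE, calibrated remainder (95 + 215) | 0.1232/0.50 = 0.246 | 0.1232/0.75 = 0.164 |
| SE, combined | 1/√(20.0 + 16.5) = 0.166 | 1/√(15.0 + 37.1) = 0.139 |

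Simulation that estimates the factor from the 80 pairs gives nearly the same: combined mean about 0.30 in both cases, with SE about 0.17 and 0.14.

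**5. Sensitivity to the key assumption.** Suppose self-report has its own effect of ±0.1 SD given actigraphic duration. In the opposite-group case the actigraphy-only and calibrated parts become 0.35 and 0.50 (or 0.25 and 0.10). In the midway case they become 0.40 and 0.433 (or 0.20 and 0.167). Weighted as in step 4, the combined estimate runs from about 0.18 to 0.42, against a true 0.30.

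**The case against.** The strongest reply is that the plan already analyses objective sleep variables, calls itself exploratory, and in its formal objective and hypothesis names no measurement method. On that view a missing calibration analysis is not an error. This largely stands: it makes the point an improvement rather than a defect that invalidates the plan.

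Several stronger readings are tempting, and the documents do not support them.
- *The self-report regression is the main estimate.* The plan names no main estimate; the gap is that the analysis testing the hypothesis is unspecified.
- *The estimate is biased towards zero.* That needs non-differential error and well-measured covariates. Step 3 of the working shows that it can go the other way.
- *The plan itself concedes 25% error.* The 75% is a recruitment assumption for a selected sample. Someone reporting 6 h and measured slightly above it may count as discordant with almost no exposure error.
- *Actigraphy should replace the Step 1 analysis.* On the assumed figures, the ratio of estimate to SE for actigraphy alone is 0.30/0.224 = 1.3 or 0.30/0.258 = 1.2. For the uncorrected Step 1 contrast it is 0.15/0.106 = 1.4 or 0.225/0.106 = 2.1. Demoting Step 1 would gain validity for objective duration but no power.

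It is also fair to say that the validation sample is limited. It omits reports outside the two bands, ages outside 40-65 and users of diabetes medication, who may differ in glycaemia. One week of actigraphy is itself an imperfect measure of habitual sleep. These limits shape the fix but do not remove the reason for it.

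**Conclusion.** The concern holds in a limited form. The rationale is about objective sleep duration, the full-sample regression can use only self-report, and the plan leaves unused the paired data that could connect that regression with the 80-person actigraphy analysis. The Step 1 coefficient may be biased for objective duration, often but not necessarily towards zero.

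No size of bias follows from the documents. The 0.35-0.75 range depends on treating the 75% as an agreement rate with non-differential error and no covariates. The gain from combining (SE about 0.17 against 0.22, or 0.14 against 0.26) depends on the assumed group sizes and on self-report having no effect of its own. Because a modest departure moves the combined estimate appreciably, the calibrated result belongs beside the planned analyses, not in their place. Label: cheap improvement.

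**What to change.** In Statistical Methods, Steps 1 and 2, keep both planned analyses and add one supplementary analysis of self-reported 6 h or less versus 7-8 h:
1. In the Step 2 participants, regress actigraphic on self-reported duration, including every covariate of the outcome model (age, sex, BMI, sleep quality, apnea risk).
2. Apply this calibration to Step 1 participants in the two report groups who have no actigraphy, and fit the HbA1c model with the calibrated duration.
3. Combine the result with the Step 2 actigraphy estimate, using the same covariates in both parts, and give a bootstrap confidence interval that repeats the calibration step.
4. Treat the version restricted to ages 40-65 without diabetes medication as the directly applicable one. The wider version needs the calibration to carry over to other ages and to medication users.
5. State the assumptions of non-differential error and transportability.
6. State that a null uncorrected self-report result will not be interpreted as evidence of no role for objective sleep duration.

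The cost is a paragraph of text and a little more analysis; no new participants, visits or assays are needed. The calibrated interval will be wider than the uncorrected Step 1 interval, and the result will rest on the stated assumptions.

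### Hypothesis 1 is about glucose tolerance, but its stated analysis uses only HbA1c and fasting values, and the Step 3 glucose and insulin curves have no stated analysis

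*Combined protocol and SAP*

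**What the plan says.** The Objectives & Hypotheses and Hypothesis sections make glucose tolerance the outcome of item 1. Background and Rationale adds that sleep is to be measured objectively: "We hypothesized that prediabetes patients with short sleep duration, as measured objectively, will have worse glucose tolerance than those with normal sleep duration".

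For Steps 1 and 2, Statistical Methods says that the sleep variables, from questionnaires and from devices, "will be analyzed to explore their relationship with HbA1c, and when available, fasting glucose and insulin levels". It continues: "To identify the independent sleep predictor of glucose tolerance status, multivariate regression analysis will be employed". That outcome is not defined. The Step 1 sample-size text points to HbA1c: "Predictors of HbA1c include age, sex and BMI", and "Sleep predictors will include sleep duration, quality and sleep apnea risk".

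Study Procedures schedules HbA1c in Step 1 and fasting glucose and insulin in Step 2. Step 3 adds half-hourly glucose, insulin and GLP-1 over three hours, in both sleep groups. The Step 3 analysis is a single sentence: "Area under the curve of GLP-1 and its peak response will be compared between short and normal sleepers".

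The Step 3 challenge is a mixed meal test in Study Design/Population/Method and in the STEP 3 eligibility paragraph. In the Step 3 procedures it is a 75-gram OGTT.

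**The concern.** Glucose tolerance ordinarily means how glucose behaves after a challenge. HbA1c and fasting values describe glycemic level, which is related but different. As written, the first hypothesis would be judged on level measures, while the data closest to it, collected in exactly the groups it compares, have no stated use.

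Two things are at stake. A report could state a conclusion on glucose tolerance that its stated analysis does not support. And if the Step 3 curves are analysed later, the summary (area under the curve, 2-hour value or peak), the adjustment and the contrast could all be chosen with the results in view.

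**Working it through.** **1. Match each step to its data and its stated analysis.**

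| Step | Glycemic data scheduled | Stated analysis |
|---|---|---|
| 1 (600 people) | HbA1c | Bivariate; regression on glucose tolerance status, undefined, apparently HbA1c |
| 2 (80 expected) | Fasting glucose and insulin | Same, when available |
| 3 (31 per group) | Serial glucose and insulin after a challenge | None for glucose or insulin; GLP-1 area and peak only |

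The only post-challenge glucose is in the row with no glucose analysis. The exposure side is in order: actigraphy and WatchPAT variables do enter the Step 1 and 2 analysis. The mismatch is in the outcome.

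**2. The plan's own Step 3 figure.** Power/Sample Size gives 31 per group, 80% power, a 35% difference in GLP-1 peak time and 10% drop-out. The SD, alpha and sidedness are not stated, so 31 cannot be reproduced. Assuming two-sided alpha 0.05 and the normal approximation, the detectable standardised difference is d = (1.960 + 0.842) × √(2/n):
- n = 31: d = 2.802 × 0.254 = 0.712, implying an SD/mean ratio of 0.35/0.712 = 0.49.
- n = 28 (31 × 0.9 = 27.9): d = 2.802 × 0.267 = 0.749, implying 0.35/0.749 = 0.47.

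The calculation concerns GLP-1 only. No power statement covers glucose.

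**3. What a Step 3 glucose comparison could show.** Unadjusted two-group t test (noncentral t), two-sided alpha 0.05, both assumed sizes:

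| | 31 per group | 28 per group |
|---|---|---|
| Difference detectable with 80% power | 0.723 SD | 0.762 SD |
| Power for a true 0.5 SD difference | 49.1% | 45.1% |
| 95% CI half-width, t × √(2/n) | 0.508 SD | 0.536 SD |

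The t-based detectable differences are slightly larger than the normal approximation in step 2, as expected. The documents give no SD for a glucose outcome, so these cannot be converted to mg/dl. The adjusted figure depends on covariate correlations that are not known.

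**4. Illustration of an unnamed outcome.** Suppose three glucose summaries (area, 2-hour, peak) were each tested at 0.05 with none named in advance. In 40,000 simulated null trials per setting, at least one was significant in about 13% with pairwise correlation 0.5, 11% with 0.7 and 8% with 0.9. The set of three and the correlations are assumptions. The range shows the mechanism and does not describe this plan.

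**The case against.** The strongest reply is that the authors use glucose tolerance loosely. Eligibility is defined by HbA1c or fasting glucose, the background moves between tolerance and glycemic control, and the sample-size text treats HbA1c as the regression outcome. On that reading Hypothesis 1 has an analysis with named predictors, and the Step 1 and 2 half of the point is terminology. This largely stands, but the wording should then be corrected in the objective and hypothesis as well as in Statistical Methods. The Step 3 glucose and insulin data would still have no stated analysis.

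Second, Step 3 is framed and sized for GLP-1, glucose and insulin may be supporting measures there, and Background and Rationale says that "the current proposed study is exploratory in nature by means of association". This also stands. It lowers the harm and rules out any demand for a larger sample. It does not explain what the serial measurements are for.

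Three stronger readings are tempting, and the documents do not support them:
- A reader might infer that the Step 3 glucose data will be left unanalysed. The plan is silent on them; it does not say that they will be set aside.
- A reader might infer that an adjusted Step 3 model must meet the plan's sizing rule. The statement that the sample should "follow a rule of 10 participants for each variable in the multivariate regression analysis" justifies the 600 in Step 1 and is not applied to Step 3.
- A reader might take 8% to 13% as the plan's error rate. The plan names no set of glucose tests, so it has no such rate.

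Finally, the meal-versus-OGTT conflict is a separate inconsistency that affects GLP-1 equally. It matters here only because the test decides what the glucose curve measures.

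**Conclusion.** The point holds. The analysis serving Objective 1 and Hypothesis 1 uses HbA1c and, when available, fasting values under an undefined outcome name. The post-challenge glucose and insulin collected in the hypothesised groups have no stated analysis. This should be corrected, but it does not undermine the study: the work is declared exploratory and the needed data are already scheduled.

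The textual finding rests on no numerical assumption. The precision figures do: two-sided alpha 0.05, 80% power, an unadjusted t test and 28 to 31 evaluable people per group. On those terms the Step 3 glucose comparison detects 0.72 to 0.76 SD and has 45% to 49% power at 0.5 SD. It can support an estimate with an interval, but a non-significant result could not be read as no difference.

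**What to change.** 1. Reconcile Study Design/Population/Method and the STEP 3 paragraph (mixed meal) with the Step 3 procedures (75-gram OGTT).
2. Add to the Step 3 analysis one glucose outcome named in advance, compared between short and normal sleepers as the post-challenge evidence for Hypothesis 1. Total glucose AUC from 0 to 180 minutes is one reasonable choice that the half-hourly sampling supports; the documents do not dictate it over 2-hour glucose. Report the difference with its 95% CI, unadjusted and adjusted for age, sex, BMI and apnea-hypopnea index. Give insulin AUC as a supporting outcome, with 2-hour glucose as well if the test is an OGTT.
3. Label this comparison exploratory and not sized for glucose. State the detectable difference with its assumptions, and say that a non-significant result is not evidence of no difference.
4. In Statistical Methods, replace the undefined outcome with HbA1c, fasting glucose and fasting insulin. Align Objective 1 and Hypothesis 1 so that Steps 1 and 2 support a statement about glycemic level and only the Step 3 data support one about glucose tolerance, or about post-meal glucose response if the test is a mixed meal.

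Cost: text changes to the protocol (items 1 and 4) and the analysis section (items 2 to 4), with no new samples or visits. The downside is two or three more reported outcomes in at most 62 people (2 × 31). They come from a subgroup (age 40 to 65, not on diabetes medication, reporting short or normal sleep) narrower than the prediabetes population of Objective 1. The report should say so.

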**STEP 3:**

Participants who complete step 2 and are confirmed to have short sleep duration and normal sleep duration by objective assessments will undergo a mixed meal test with measurements of GLP-1, glucose and insulin.

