### **STEP 3**

After confirming the sleep duration by Actiwatch, both short and normal sleepers will undergo a 75-gram OGTT after an overnight fasting. Serum glucose, insulin and GLP-1 will be collected every 30 minutes for 3 hours. Expected participants in each group = 31

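### Step 2's 80 participants at the stated 75% concordance give an expected 60 for Step 3, not the 62 it requires

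*Combined protocol and SAP*

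**What the plan says.** The power and sample-size text under Statistical Methods justifies Step 2 in one sentence: 80 was chosen to "ensure adequate recruitment for STEP 3 which requires 62 participants, with a 75% concordance rate of self-reported and objectively measured sleep duration".

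The same figures appear elsewhere:

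- Study Design/Population/Method, on Step 2: "This step will serve as a screening for step 3 (expected N= 80".
- Study Procedures, Step 2: participants "will undergo objective sleep measurements as follow. Expected participants = 80".
- Study Procedures, Step 3: "Expected participants in each group = 31", which makes 62 in total.

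The entry rule for Step 3 is that those who finish Step 2 and are "confirmed to have short sleep duration and normal sleep duration by objective assessments will undergo a mixed meal test".

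The 10% dropout and 80% power are attached to the 31 per group in Step 3. No other yield or allowance is given for Step 2.

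**The concern.** A screening size should follow from the number required and the expected yield. Here all three figures stand in one sentence, and multiplying the first by the third does not give the second. The gap also runs the wrong way: 80 is too few, although it is presented as securing 62. The wording promises more than a screening size equal to required number divided by yield could deliver in any case, because the number confirmed will vary around its mean.

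At stake is whether a reader can reproduce the Step 2 size, and a small part of the Step 3 margin. There is also a gap in the entry rule: the plan does not say what happens to a participant whose actigraphy disagrees with the self-report.

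**Working it through.** **Inputs.** Step 2 size 80, Step 3 requirement 62 and concordance 75% (Statistical Methods); 31 per group (Study Procedures, Step 3); 10% dropout and 80% power (Statistical Methods, Step 3). Concordance is read as the fraction of Step 2 that enters Step 3, in line with the confirmation rule for Step 3.

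**1. Attempt to reproduce 80.** Required screening size = required entrants / yield.

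- 62 / 0.75 = 82.7, so 83. The stated 80 is not reproduced.
- By group: 31 / 0.75 = 41.3, so 42 per group, 84 in total.
- 60 / 0.75 = 80, so 80 matches a requirement of 60 (30 per group), not 62.
- 62 x 1.25 = 77.5, so 78. This is an incorrect inflation that lands near 80. Whether it was used cannot be known.
- Taking 62 net of 10% dropout: 56 / 0.75 = 74.7. This does not give 80 either, and the plan states the requirement as 62.

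**2. Expected yield from 80.**

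- 80 x 0.75 = 60.
- Shortfall: 62 − 60 = 2, or 1 per group; 2/62 = 3.2%.
- Concordance needed for 80 to yield 62: 62/80 = 77.5%.

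**3. Chance of reaching the target.** Assume independent 75% concordance and exclusion of discordant participants (binomial).

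| Step 2 size | P(at least 62 in total) | P(at least 31 in both groups, equal split assumed) |
|---|---|---|
| 80 | 0.36 | 0.19 |
| 84 | 0.65 | 0.42 |

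**4. Effect on power.** The plan gives no alpha, sidedness or SD. Assume alpha 0.05 and back-solve the effect from the plan's own 80% power.

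- Evaluable per group as planned: 31 x 0.9 = 27.9, about 28.
- Evaluable per group from 30 entrants: 30 x 0.9 = 27.
- Normal formula, two-sided, with 80% power at 28 per group: power at n = Φ[(1.960 + 0.842) x √(n/28) − 1.960]. At n = 27 this is Φ(2.751 − 1.960) = Φ(0.791) = 0.786.
- Across one- and two-sided tests, t and normal formulas, and 27.9 or 28 as the base, power at 27 is 78.5% to 78.9%, a loss of 1.1 to 1.5 points.
- If all 30 per group complete, the same assumptions give about 82% to 83%. The shortfall therefore uses 1 of the roughly 3 per group allowed for dropout (31 − 28 = 3).

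**The case against.** The strongest objection is that the 75% is called a concordance rate, not a yield. The Study Procedures text forms the groups after actigraphy, so a person who reported normal sleep but is objectively short might be counted as a short sleeper. Only 2 of the 20 expected discordant participants would have to be placed this way to reach 62 in total. This cannot be ruled out, but the documents do not say it. The Step 3 entry rule speaks of confirmation, and the Step 2 justification uses concordance as its only yield figure. If reassignment were intended, 75% would not be the relevant input and the justification would still need rewriting.

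Second, 80 is described as expected in two places, and nothing stops Step 2 from continuing beyond it. At the plan's 20–25% prevalence, 600 people include 120 to 150 self-reported short sleepers, before the age and medication limits. It is fair that 80 is not a stated cap. It remains the figure offered as sufficient for 62, and an expected 80 gives an expected 60.

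Third, 75% is a round planning value and the gap is of rounding size. This stands as an argument about weight. It does not remove the mismatch, since rounding for a recruitment target should go up.

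Finally, 30 entrants per group still exceed the 28 or so evaluable participants needed, and the power figures rest on assumed inputs. Both points stand. The supportable statement is a loss of about one point of power, and this is not evidence that Step 3 is underpowered.

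**Conclusion.** The concern holds as a minor inconsistency. The mismatch needs no outside figure, and nothing in the protocol reconciles 80, 75% and 62. Its size is 2 fewer people in Step 3, or 3 too few in Step 2.

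The arithmetic is certain. That the shortfall would actually occur rests on three conditions: discordant participants are excluded, concordance is 75%, and Step 2 stops at 80. The power effect also rests on an assumed alpha of 0.05 and an effect back-solved from the plan's own claim.

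**What to change.** Make the three figures agree, and replace the claim that 80 will *ensure* the Step 3 number with *expected to yield*. Any one of these would do:

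1. **Keep 80.** State Step 3 as an expected 30 per group, about 27 evaluable after 10% dropout, with power restated accordingly. This costs only a slightly less favourable power figure.
2. **State Step 2 as about 84**, 42 per self-reported group. Note that this meets 31 per group on average only; under the binomial assumptions above it reaches 31 in both groups about 42% of the time. It adds 4 sets of actigraphy and WatchPAT recordings.
3. **Continue Step 2 until 31 per group are confirmed**, with an expected total of about 83. This is the only option that secures the number, provided enough eligible Step 1 participants are available. It adds about 3 sets of recordings on average, and the total is not fixed in advance.

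Options 2 and 3 draw on people already in Step 1. Whichever is chosen, add one sentence saying whether discordant participants are excluded from Step 3 or assigned to the group that matches their objective sleep duration. If they are reassigned, base the Step 2 size on the yield that follows from that rule.
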